Methodology (study design)	
A multi-center, randomized, open-label, active-controlled study of the efficacy and safety of conversion from long-acting ESA (Mircera) to vadadustat TIW for the maintenance treatment of anemia in hemodialysis patients. Following a Screening period of up to 8 weeks (56 days), subjects who meet all inclusion and none of the exclusion criteria, Mircera will be discontinued and subjects will be randomized 1:1:1 to vadadustat 600 mg TIW, vadadustat 900 mg TIW, or to remain on Mircera according to the dialysis center's protocol.
 
Randomization will be stratified by dialysis organization:
 
Following randomization, there will be 2 periods during the study:
 
 Conversion and Maintenance Period (Weeks 0 to 52): conversion to vadadustat TIW or to remain on Mircera (Weeks 0 to 20). There will be a primary efficacy evaluation period (Weeks 20 to 26) and a secondary efficacy evaluation period (Weeks 46 to 52). Safety Follow-up Period (Early Termination [ET] and Follow-Up): post-treatment safety follow up visit (ET/End of Treatment [EOT] +4 weeks) either in person or via telephone.
Study Duration	Individual subjects will participate in the study for up to 64 weeks, including a Screening Period of up to 8 weeks, a 52-week Treatment Period and a 4-week Safety Follow-Up Period.
Key Inclusion and Exclusion Criteria	Subjects must meet the following inclusion criteria: 
 ≥18 years of age. Receiving chronic, outpatient in-center hemodialysis TIW for end-stage kidney disease for at least 12 weeks prior to Screening Visit (SV)1. Currently maintained on Mircera (≤250 µg/month) with at least 2 doses

[figure not shown]

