6.0 STUDY POPULATION

6.1 Inclusion Criteria

Subjects must meet the following inclusion criteria:

1. ≥ 18 years of age.
2. Receiving chronic, outpatient in-center hemodialysis TIW for end-stage kidney disease for at least 12 weeks prior to SV1.
3. Currently maintained on Mircera (≤ 250 $\mu\text{g}/\text{month}$) with at least 2 doses received within 8 weeks prior to SV2.
4. Mean screening Hb between 8.5 and 11.0 g/dL (inclusive), as determined by the average of 2 Hb values measured by the central laboratory at least 4 days apart between SV1 and SV2.
5. Serum ferritin ≥ 100 ng/mL and transferrin saturation (TSAT) $\geq 20\%$ during Screening.
6. Folate and vitamin B₁₂ measurements \geq lower limit of normal during Screening.

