Mircera assigned subjects will be administered IV Mircera at the hemodialysis unit according to the dialysis center's protocol.

Dose adjustments will be guided by central laboratory Hb concentrations throughout the study to determine if vadadustat or Mircera doses will be adjusted, interrupted, or maintained. Mircera dosing will be based on standard of care laboratory measures according to the dialysis center's protocol. Vadadustat dose adjustment will be based on the guidelines in the protocol Section 7.1.2.

The minimum dose of vadadustat will be 300 mg TIW (1 tablet TIW) and the maximum dose will be 1200 mg TIW. Subjects whose dose of vadadustat is interrupted due to elevated Hb will continue in the study. Unless contraindicated, treatment will be resumed whenever possible and assessed at every study visit following study drug interruption.

Clinical evaluations will be conducted during the course of the study based on the schedule of activities in the protocol Table 1. If the evaluations will occur on a hemodialysis day, the clinical evaluations should be completed before dialysis, if applicable.

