5.3 OTHER EFFICACY ENDPOINTS

Other endpoints include the following:

- Proportion of subjects having a Hb value within the target range (10.0 to 11.0 g/dL) during the primary evaluation period (Weeks 20 to 26).
- Proportion of subjects having a Hb value within the target range (10.0 to 11.0 g/dL) during the secondary evaluation period (Weeks 46 to 52).
- Proportion of subjects having average Hb value within the target range (10.0 to 11.0 g/dL) during the primary evaluation period (Weeks 20 to 26)
- Proportion of subjects having average Hb value within the target range (10.0 to 11.0 g/dL) during the secondary evaluation period (Weeks 46 to 52)
- Mean change from baseline and percentage change from baseline in the primary efficacy period (PEP) and secondary efficacy period (SEP) for iron-related parameters
- Proportion of subject receiving rescue by analysis periods.
- Proportion of subjects receiving RBC transfusions by analysis periods.
- Proportion of subjects receiving ESA medication by analysis periods.
- Time to first rescue by narrow and broad (include any rescue, ESA, and RBC respectively)
- Proportion of subjects who received any IV iron therapy by analysis period)
- Mean weekly IV dose elemental iron by analysis period and route of administration
- Mean change in serum glucose and lipid parameters between Baseline and the PEP (Weeks 20 to 26) and SEP (Weeks 46 to 52)
- Mean change in iron metabolism (including iron, hepcidin, ferritin, transferrin saturation [TSAT], total iron binding capacity [TIBC]) between Baseline and the PEP (Weeks 20 to 26) and SEP (Weeks 46 to 52)

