6.11.4.4 Definition of Rescue

The eCRF collects reasons for ESA medication and RBC transfusion. An Event is considered as rescue only when the event occurred between first dose date to permanent study treatment discontinuation. The series of rescue definitions are defined as follows:

- Narrow:
 - For RBC transfusion, when “Low Hemoglobin” is the reason indicated on the eCRF.
 - For ESA medication:
 - Vadadustat arm: the reason of ESA usage is the subject’s Hb less than 9.0 g/dL.
 - Mircera arm: two scenarios are defined as below:
 - i. the reason of other ESA or Mircera usage is the subject’s Hb less than 9.0 g/dL or Mircera dose increase at least 50%.
 - ii. the reason of other ESA or Mircera usage is the subject’s Hb less than 9.0 g/dL or Mircera dose increase at least 100%.
- Broad:
 - Any RBC transfusion.
 - For ESA medication:
 - Vadadustat arm: any ESA usage.
 - Mircera arm: two scenarios are defined as below:
 - i. Any other ESA usage, or Mircera usage due to the subject’s Hb less than 9.0 g/dL or Mircera dose increase at least 50%.
 - ii. Any other ESA usage, or Mircera usage due to the subject’s Hb less than 9.0 g/dL or Mircera dose increase at least 100%.

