6.11.4.4.1 Analysis of Rescue

The number and percentage of subjects receiving rescue by rescue type, treatment group and analysis period will be summarized. Confidence interval will be 95% CI for these proportions along with the difference in proportions as well as the odds ratio. A Mantel-Haenszel test stratified by the dialysis organization will be used to calculate the 95% CI for the statistics of treatment comparison.

Time to first rescue therapy administration by narrow and broad definitions separately will be estimated using the Kaplan-Meier product-limit method and log rank test. Subjects without events will be censored at last dose date. The hazard ratio and corresponding 95% CI for the comparison of vadadustat to Mircera will be estimated using a Cox proportional hazards model, with treatment group, randomization stratification factor (dialysis organization), and baseline Hb as covariates. Kaplan-Meier plots of time to first rescue will be provided.

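### Time to first rescue counts events up to treatment discontinuation but censors event-free subjects at last dose, a mismatch that lasts longer in the Mircera arm

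*SAP*

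**What the plan says.** SAP 5.3 lists time to first rescue, by narrow and broad definitions and for any rescue, ESA and RBC transfusion, among the other efficacy endpoints.

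- **Event window** (SAP 6.11.4.4): a rescue counts only when "the event occurred between first dose date to permanent study treatment discontinuation".
- **Censoring** (SAP 6.11.4.4.1): "Subjects without events will be censored at last dose date".
- **Estimate** (SAP 6.11.4.4.1): "The hazard ratio and corresponding 95% CI for the comparison of vadadustat to Mircera will be estimated using a Cox proportional hazards model", with a log-rank test and Kaplan-Meier plots. SAP 6.11.4.4.2 carries the same analyses over to RBC transfusion. SAP 6.11.4.4.3, headed ESA rescue, repeats that sentence and presumably means ESA.
- **Mircera interval**: not fixed on study. SAP 3.1 says "Mircera assigned subjects will be administered IV Mircera at the hemodialysis unit" and leaves the regimen to the center. Entry requires Mircera maintenance "with at least 2 doses received within 8 weeks prior to SV2" (Protocol 6.1).
- **Vadadustat**: taken on dialysis days, three times a week (Protocol 7.4), with temporary interruptions allowed (Protocol 8.1.1).

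**The concern.** A time-to-event analysis needs every subject to be at risk over the same period in which an event would have been counted. Here the length of follow-up depends on the outcome. Between last dose and discontinuation, a subject with a rescue stays in the analysis up to that event, while a subject without one has already left the risk set. The hazard in that stretch is overstated.

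The stretch differs by arm. Dosing three times a week leaves a gap of about 2 to 3 days. A long-acting agent can leave a gap of up to one dosing interval, even in a subject who completes 52 weeks without incident. If rescue can happen on any day, the Mircera hazard is inflated more than the vadadustat hazard and the hazard ratio moves toward vadadustat. RBC transfusion is the component to watch: a transfusion is not a Mircera dose, and transfusion proportions are secondary safety endpoints in Protocol 4.7.

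Two other SAP rules treat the end of treatment differently. The compliance formula in SAP 6.10 adds one dosing interval after the last Mircera record. The time-to-discontinuation analysis in SAP 6.5 censors completers at study completion, not at last dose.

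**Working it through.** The plan gives no event count, hazard ratio or power for this endpoint, so there is no stated figure to reproduce.

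**Inputs from the documents.** 52 weeks of treatment; about 150 subjects per arm, hence 300 against 150 with vadadustat pooled; 30% dropout (SAP 3.3); vadadustat three times a week.

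**Assumptions.** Constant hazard; true hazard ratio 1; one-year rescue probability 10% to 50%; dropout 10% to 40%; Mircera every 2 or 4 weeks. A dosing grid starting at Day 1 is plausible because Protocol 7.1.2 asks that randomization coincide with the next expected Mircera dose. On a 28-day grid the doses fall on Days 1, 29, ..., 337. The Week 52 target is Day 364, so a completer not dosed at that visit is censored 364 − 337 = 27 days early.

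**Hand check (30% rescue, 30% dropout, 4-weekly Mircera, no Week 52 dose).**

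1. Weekly rate for each process: −ln(0.70)/52 = 0.00686.
2. Mean weeks at risk: (1 − 0.70 × 0.70)/(2 × 0.00686) = 0.51/0.01372 = 37.2.
3. Share with rescue: 0.51/2 = 0.255, so 0.745 are event-free.
4. Simulated mean gap in event-free subjects: 3.31 weeks for Mircera, 0.17 for vadadustat. Time lost per subject: 0.745 × 3.31 = 2.47 and 0.745 × 0.17 = 0.13 weeks.
5. Events are unchanged, so the rate ratio is (37.2 − 2.47)/(37.2 − 0.13) = 34.73/37.07 = 0.94, against 0.93 simulated.

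The Cox estimate in the same run is 0.91. It lies further from 1 because the lost time for completers is concentrated in the last weeks, when few Mircera subjects remain in the risk set.

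**Large-sample simulation (600,000 against 300,000), true hazard ratio 1.**

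| Scenario | SAP rule | Both windows end on one date |
|---|---|---|
| Rescue at any time, 4-weekly, no Week 52 dose | 0.89 to 0.93 | 0.99 to 1.01 |
| Rescue at any time, 2-weekly, no Week 52 dose | 0.95 to 0.96 | 1.00 to 1.01 |
| Rescue at any time, 4-weekly, dose at Week 52 | 0.98 to 0.99 | 0.99 to 1.00 |
| 50%, 80%, 100% of Mircera-arm rescues are Mircera doses (4-weekly, 30% rescue) | 0.96, 1.00, 1.02 | both at last dose: 1.01, 1.01, 1.02; both at discontinuation: 1.04, 1.07, 1.09 |
| All vadadustat early stoppers first interrupt for 0 to 4 weeks, no Week 52 Mircera dose | 0.92 | 1.00 |
| Same, with a Week 52 Mircera dose | 1.01 | 1.01 |

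If the Mircera grid has a random phase relative to Day 1 (30% rescue, 30% dropout), the SAP rule gives about 0.96 for 28-day and 0.98 for 14-day dosing.

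**Scale.** At 450 subjects and 25.5% with rescue there are about 115 events, split 77 and 38. The standard error of the log hazard ratio is √(1/77 + 1/38) = 0.20. A hazard ratio of 0.90 is −0.105 on the log scale, about half a standard error.

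**The case against.** **The discontinuation date is not defined.** Protocol 8.1.2 puts the ET visit at the time of permanent discontinuation with follow-up four weeks later; Protocol 9.1.4 times the same follow-up from the last dose. Together these nearly equate discontinuation with last dose for early stoppers, and for them the windows could coincide. Much of the SAP appendix text is blacked out, so a definition may exist there. This stands for early stoppers. It does not help completers: they have no permanent discontinuation date, and SAP 3.1 defines completion as treatment through Week 52.

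**Mircera doses can be the events.** Under SAP 6.11.4.4, Mircera-arm ESA rescue includes Mircera given for low Hb and Mircera dose increases of at least 50% or 100%. Such an event cannot follow the last Mircera dose. This stands. A reader might infer that the rule favours vadadustat by construction in every rescue analysis; the documents do not support that for any-rescue or ESA rescue.

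**The worst case needs special conditions.** A reader might also infer that the Mircera Kaplan-Meier curve would collapse to zero near Week 52. That needs every Mircera subject on one aligned 28-day grid with no dose near Week 52. The documents fix no such schedule.

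**Vadadustat has gaps too.** Interruption before a permanent stop opens the same gap in the vadadustat arms. This stands, and in the runs above it offsets only a small part of the largest bias.

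**The endpoint is minor.** It carries no margin or planned formal claim, and the rescue proportions in SAP 6.11.4.4.1 do not use the censoring date. This stands and limits the weight of the point.

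**Conclusion.** As written, the event window and the censoring date do not match, most clearly for completers. For RBC transfusion and non-Mircera ESA rescue the likely result is a hazard ratio about 1% to 11% too low, toward vadadustat. The low end applies when a Mircera dose falls at Week 52, the high end to 4-weekly dosing from Day 1 with no such dose. For any-rescue and ESA rescue the bias shrinks to nil or slightly reverses as more Mircera-arm rescues are themselves Mircera doses.

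Direction and size rest on assumed Mircera intervals of 2 to 4 weeks, a constant hazard, and discontinuation being later than last dose. At most the bias is about half a standard error. The Hb analyses and the rescue proportions do not depend on it. It is worth correcting before database lock because the rule is wrong as stated and cheap to repair, but it does not threaten the trial's main conclusion.

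**What to change.** In SAP 6.11.4.4.1, define one end-of-risk date that applies in both arms and covers completers, and use it for both event counting and censoring:

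- **RBC transfusion:** the permanent-discontinuation date for early stoppers and the EOT (Week 52) visit date for completers. State how the discontinuation date is derived.
- **Any-rescue and ESA rescue:** end both event counting and censoring at last dose. The simulated hazard ratio is then about 1.00 to 1.02.

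Moving only the censoring date to discontinuation or EOT for every component looks simpler, but it overcorrects the analyses in which Mircera doses are events (1.04 to 1.09 above).

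The cost is one or two sentences and one derived date per component. The downside is that some events after last dose leave the any-rescue and ESA time-to-event analyses, so their counts can differ from the rescue proportion tables. One source of such events was not simulated: Protocol 7.5.5.2 requires vadadustat to be interrupted during ESA rescue, so an ESA rescue begun after a last vadadustat dose that is never resumed would be dropped. Tabulate dropped events by arm, and show a sensitivity analysis with both windows ending at discontinuation or EOT. The proportion tables need no change.

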Multiple doses of up to 900 mg daily for up to 10 days and single doses of 1200 mg have been examined in healthy subjects. Vadarustat demonstrated dose-proportional PK and dose-dependent serum EPO concentrations that returned to baseline levels with treatment cessation. A higher incidence of adverse events (AEs) in the gastrointestinal System Organ Class (SOC) – nausea, diarrhea, abdominal pain, dyspepsia – was observed in groups treated with 700, 900, or 1200 mg compared with lower vadarustat doses or placebo. Most AEs were mild to moderate, short-lived (1 or 2 days), and assessed as unrelated by investigators. No AEs led to study withdrawal, and no serious adverse events (SAEs) were reported in healthy subjects. No clinically meaningful changes or abnormalities in vital signs, safety laboratory studies, or electrocardiogram (ECG) parameters were reported.

A 16-week, open-label, multicenter, Phase 2 study evaluated vadarustat in 94 subjects receiving chronic hemodialysis previously maintained on epoetin alfa and intravenous (IV) iron from the 3 months prior to Screening. Epoetin alpha was discontinued and subjects were assigned to 1 of 3 vadarustat dose cohorts: 300 mg QD, 450 mg QD, or 450 mg TIW. Dosing was fixed for the first 8 weeks; for the subsequent 8 weeks dose was adjusted from 150 to 600 mg according to Hb response based upon a dose adjustment algorithm. Sixty-nine of the 94 subjects completed the study. The primary endpoint was the mean Hb concentration change from pre-treatment average (Screening Visit 1 [SV1], Screening Visit 2 [SV2], and Baseline Visit) to mid-study (Weeks 7 to 8) and end-of-study (Weeks 15 to 16) and was analyzed using observed Hb values (no imputation for missing data). No statistically significant mean change in Hb from pre-treatment average was observed for either of the 2 time points for any of the three treatment groups.

Among subjects randomized to an initial dose of 300 mg QD, 450 mg QD, or 450 mg TIW, 0% (0 of 30), 3% (1 of 33), and 19% (6 of 31) of subjects withdrew from the study due to worsening anemia, respectively. In a sensitivity analysis using last observation carried forward for the primary efficacy endpoint, no significant mean change in Hb from pre-treatment levels was observed in the 300 mg daily dosing group. At Weeks 15 to 16, modest, statistically significant mean decreases were observed in the 450 mg daily and 450 mg TIW dosing groups.

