8.1.2 Permanent Discontinuation of Study Medication

Subjects who permanently discontinue study medication prior to study completion will not continue in the study. These subjects are to have their ET visit at the time of permanently discontinuing study medication and perform a 4-week safety follow-up after ET visit.

Subjects may permanently discontinue study medication for any of the following reasons:

- AE
- Investigator's discretion
- Subject withdrawal of consent
- Lack of efficacy
- Lost to follow up despite reasonable efforts by the Investigator to locate the subject
- Death
- Other reasons (pregnancy, kidney transplantation, specific reasons to be documented by the Investigator)

Lack of efficacy is defined as an inadequate response to vadadustat in the Investigator's opinion.

Subjects who undergo a solid organ (including kidney), hematopoietic stem cell, or bone marrow transplantation will have vadadustat permanently discontinued.

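### Subjects who stop for worsening anemia before any rescue are non-events or censored in the rescue analyses, so the comparison may favor vadadustat by an unknown amount

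*SAP*

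**What the plan says.** SAP 6.11.4.4 limits what can be a rescue: "An Event is considered as rescue only when the event occurred between first dose date to permanent study treatment discontinuation". This applies to the narrow and the broad definition and to both arms. SAP 6.11.4.4.1 then plans two analyses. For proportions, "The number and percentage of subjects receiving rescue by rescue type, treatment group and analysis period will be summarized", with stratified Mantel-Haenszel intervals. For time to first rescue it plans Kaplan-Meier, log-rank and Cox, and "Subjects without events will be censored at last dose date".

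Protocol 8.1.2 lists lack of efficacy among the reasons for permanent discontinuation and adds: "Lack of efficacy is defined as an inadequate response to vadadustat in the Investigator's opinion". It gives no matching definition for Mircera. After such a stop, "Subjects who permanently discontinue study medication prior to study completion will not continue in the study"; what remains is an early termination visit and the 4-week safety follow-up.

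In the Mircera arm, SAP 6.11.4.4 counts a Mircera dose increase of at least 50% (first scenario) or at least 100% (second scenario) as rescue. An increase in vadadustat dose is not counted.

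**The concern.** Kaplan-Meier, log-rank and Cox analyses need censoring that carries no information about the event. A subject taken off treatment because hemoglobin is falling is more likely than others to have needed an ESA or a transfusion soon afterwards. Censoring that subject at the last dose treats those who remain as representative of those who left. In the proportions the same subject stays in the denominator as not rescued.

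The rule is worded identically for both arms, so it distorts the comparison only if anemia-related stopping differs between them. Two earlier studies in Protocol 3.4 make that plausible. In a Phase 2 hemodialysis study the three-times-weekly cohort had the highest withdrawal: "and 19% (6 of 31) of subjects withdrew from the study due to worsening anemia", against 0 of 30 and 1 of 33 in the two daily cohorts. In a later conversion study 60.5% completed treatment on vadadustat and 88.9% on epoetin. The present trial is open-label, so the choice between rescuing a subject and stopping treatment is made with the arm known.

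At stake are the rescue proportions, the rescue-free curves and the rescue hazard ratio, which SAP 5.3 places among the other efficacy endpoints.

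**Working it through.** The documents give no expected rescue rate, margin or power for rescue, so there is no planned figure to reproduce. The only power statement belongs to the primary hemoglobin test and does not enter here.

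**Inputs from the documents**
- About 150 subjects per arm (SAP 3.3). With the vadadustat groups combined as in SAP section 7: 300 against 150.
- Earlier withdrawal for worsening anemia (Protocol 3.4): 1/33 = 3.0% on 450 mg daily; 6/31 = 19.4% on 450 mg three times weekly.

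**Assumptions**
- On-treatment rescue of 20% in both arms (5% to 30% also tried).
- A middle stop rate of 10%.
- No anemia-related stops on Mircera.
- No vadadustat stopper rescued before stopping.

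**Proportions under the SAP rule.** 60/300 − 30/150 = 0.0 points. SE = √(0.2 × 0.8/300 + 0.2 × 0.8/150) = 0.040. The 95% CI is −7.8 to 7.8 points.

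**Proportions with unrescued anemia stops counted as failures**

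| Stop rate | Stops in 300 | Vadadustat failures | Difference, points (95% CI) |
|---|---|---|---|
| 3% | 9 | 69/300 = 23.0% | +3.0 (−5.0 to 11.0) |
| 10% | 30 | 90/300 = 30.0% | +10.0 (1.8 to 18.2) |
| 19.4% | 58 | 118/300 = 39.3% | +19.3 (10.9 to 27.8) |

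The shift equals stops/300, so it stays between about 3 and 19 points whatever rescue rate from 5% to 30% is assumed.

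**Time to event.** Assume constant hazards and anemia failure by Week 52 of 39% on vadadustat (20% plus about 19%) and 20% on Mircera. The hazard ratio for all failures is ln(0.61)/ln(0.80) = 0.494/0.223 = 2.2. If a share q of vadadustat failures stop treatment instead of being rescued, the rescue hazard that the SAP rule sees is (1 − q) times the failure hazard:
- q = 0.25: 0.75 × 2.215 = 1.66
- q = 0.50: 0.50 × 2.215 = 1.11
- q = 0.75: 0.25 × 2.215 = 0.55

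A simulation of 300 trials with 300 against 150 subjects and 20% other dropout gave 1.72, 1.10 and 0.55. Even the direction of the reported hazard ratio depends on q, which the documents do not give.

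**Event window against censoring date.** Events count up to permanent discontinuation, but event-free subjects are censored at last dose. Protocol 7.5.5.2 interrupts vadadustat while a rescue ESA is given, so a counted rescue can fall after the last dose if vadadustat is not restarted. An event-free subject in the same interruption who then stops for good has already left the risk set.

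**Is it handled elsewhere?** SAP 6.5 analyzes time to treatment discontinuation and tabulates reasons, but does not combine either with rescue. The treatment-policy estimand in SAP 6.11.1 concerns hemoglobin only. The visible text has no composite, competing-event or post-discontinuation analysis of rescue.

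**The case against.** The strongest defense is that ending the window at permanent discontinuation has a sound reason. Every subject enters needing an ESA. Someone who stops vadadustat for an adverse event, a liver rule or a transplant, or who completes Week 52, may resume an ESA as ordinary care. The broad definition counts any ESA use in the vadadustat arm, so counting all ESA use through the 4-week follow-up would turn routine resumption into rescue in that arm and bias against vadadustat. Capture is a further problem: the schedule of activities records transfusions and ESA rescue during the treatment period, and the follow-up visit may be by telephone. This stands, and it rules out simply lengthening the window.

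It is also true that SAP 6.5 shows reasons for discontinuation by arm, so a careful reader can set them beside the rescue table. That informs the reader but leaves the rescue estimates as they are.

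A reader might infer that every vadadustat subject who stops for anemia is recorded as never rescued, or that the comparison is necessarily biased toward vadadustat and more so the worse the drug works. The documents do not support either. Protocol 7.5.5.2 allows ESA rescue on study, generally at hemoglobin below 9.0 g/dL, with vadadustat interrupted and later resumed. Those rescues count, so poorer efficacy can also raise recorded rescue. Lack of efficacy is one of several listed reasons to stop, and its frequency is not given.

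Nor can 19 points be read as a forecast. That earlier cohort received 450 mg three times weekly, fixed for 8 weeks and then adjusted from 150 to 600 mg. This trial starts at 600 or 900 mg, allows an early increase and titrates up to 1200 mg.

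**Conclusion.** The concern holds in a limited form. Subjects who permanently stop for lack of efficacy or worsening anemia before any rescue are non-events in the proportions and informatively censored in the time-to-event analyses. The comparison may favor vadadustat if such stopping is more common there. Counting large Mircera dose increases as on-treatment rescue would add to that, although it is a separate feature of the definition.

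The range of about 3 to 19 points is an illustration. It rests on equal rescue rates, no such stops on Mircera, no rescue before stopping, and withdrawal rates from other regimens. At the low end the interval still spans zero. The rescue endpoints carry no margin or formal hypothesis. The primary hemoglobin analysis does not use the rescue window, so no primary conclusion changes. The case is for a supplementary analysis and one correction to the censoring date.

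**What to change.** In SAP 6.11.4.4.1:

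1. Keep the on-treatment rescue analysis as planned.
2. Add a supplementary endpoint: first rescue, or permanent discontinuation for lack of efficacy or worsening anemia, whichever comes first. Report it for the proportions and for time to event. Fix before database lock which discontinuation reasons qualify, and apply them in the same way to both arms, since the protocol words lack of efficacy for vadadustat only.
3. Alternatively, show the cumulative incidence of rescue with such discontinuation as a competing event. Plot both incidences, because the rescue curve alone would still look low where many subjects stop.
4. Censor event-free subjects at permanent discontinuation, so that the risk set ends where the event window ends.
5. Do not count all ESA use through the 4-week follow-up.

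The cost is SAP wording, one extra row per rescue table and one extra curve. SAP 6.5 already summarizes reasons for discontinuation, and the composite needs no data after the stop. The drawback is that investigator-judged reasons in an open-label trial enter the endpoint, which is why it should stay supplementary.
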